6.1.15. Adverse Events

The information obtained during weekly subjects questioning, review of subject's compliance record, physical examinations, vital signs measurements, blood testing, and by any other means will be evaluated in light of baseline medical data and thus provide the basis for adverse events identification and grading.

The trial will proceed within a cohort and from one cohort to the next as long as no more than one subject experiences intolerable side effects and based on the decision made by the PI. Proceeding from one subject to the next will be based on the decision made after reviewing all safety data collected by Day 7 within 2 ± 1 d of the last dosed subject in each cohort.

The AEs reported during the trial will be graded (see Section 9), documented, and assessed in light of their clinical significance and relation to investigational product. In addition, the following information regarding the AE must be obtained: AE description, start date, end date (if applicable) or ongoing, severity, seriousness, relationship to study drug, outcome (e.g., resolved / unresolved), and action taken (e.g., concomitant medication). The sponsor or the sponsor representative will provide information regarding serious adverse event (SAE) expectedness based on data included in the IB. AE monitoring will be conducted throughout subject's participation up to 56 days after injection.

6.1.16. Evaluation of Response

Evaluation of response will be conducted on Day 7 and every 7 days thereafter till Day 28.

6.1.16.1. Evaluation of Primary Endpoints

6.1.16.1.1. Safety and Tolerability Monitoring

For determination of the study's primary end point, evaluation of safety and tolerability will be conducted according to definitions and guidelines below.

Safety and tolerability will be assessed by the study medical staff (e.g., PI, site coordinator, and study nurse) and the study subjects on the basis of the following:

1. AEs and SAEs, including severity, relation to study treatment and classification by whether or not these events comprise intolerable side effects.
2. Physical exams, Draize score and vital signs measurements.
3. Urine testing.
4. Blood laboratory testing for changes in hematology and chemistry values.
5. ECG

6. Subjects questioning - full medical history during screening, routine AE reporting, tolerability monitoring and through review of subject's analgesics use diary.

6.1.16.2. Evaluation of Secondary Endpoints

6.1.16.2.1. Local Fat Reduction for Lipedema Subjects

For lipedema subjects, local reduction in fat mass will be evaluated by measurement of the circumference of the leg above the knee. A local fat reduction is defined as a reduction (compared to baseline) in the circumference of the leg above the knee.

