Results:

This was a dose escalation exploratory clinical trial of RZL-012, a first-in-class, new chemical entity.

RZL-012 was generally found to be safe in all cohorts. There were no clinically significant changes in vital signs, ECG and almost all blood laboratory tests. Most adverse events (AEs) associated with RZL-012 injection occurred confined to the injection site and were transient. Biopsy from the injected site revealed no damage to the skin 56 days following RZL-012 injection. The only significant local AE was an abscess in one subject in the lower abdomen on the injected side, but at a considerable distance from the site of injection.

In another patient, a severe elevation of alanine aminotransferase (ALT) blood levels and a moderate elevation of AST blood levels were seen 14 days following injection. This elevation was transient (resolved within 14 days). In light of the pre-clinical findings (increased AST blood levels in female rats sacrificed on Day 2 following RZL-012 injection) and in light of the findings in this clinical trial, Raziel therefore plans to monitor closely (on 24hr, Day 3, Day 7, Day 14, Day 21, Day 28 and will follow further if necessary) liver functions in the next clinical trial. There were no other systemic clinically significant AEs.

The exploration of thermogenesis induction by RZL-012 in humans was successful. A raise in temperature at the injection site was mostly evident in cohort 3 (the highest dose) at Day 14 or Day 21 following injection in RZL-012 treated subjects only. This change in temperature was captured and recorded by the infra-red camera.

Although not statistically significant, a drop in the change from baseline in SFM ratio (treated/control) over time by MRI in RZL-012 treated subject of cohort 3 was evident in 5 of 6 treated subjects. The drop in subcutaneous fat associated with a drop in weight (more than 1 kg) and Body Mass Index (BMI) when compared to baseline and is evident in 4 of 6 RZL-012 treated subjects of cohort 3 on Day 28 and/or Day 56, while controls gained weight and increased BMI.

Biopsy did not yield enough tissue (because punch biopsy did not penetrate deep enough to reach the remodeled tissue), and therefore, it was not possible to demonstrate that thermogenesis is due to adipose tissue remodeling.

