6.1.13. Leg Circumference

Leg circumference measurement will be conducted at Screening (performed 14 through 2 days prior to baseline) to ensure compliance with study inclusion criteria and at Day 0 (before injection) to establish a baseline. Additional leg circumference measurements will be performed on Day 28 and 56.

The subject will be instructed to remove all garments from the legs and stand upright barefoot. The technician will stand on the subject's side and will palpate the knee area to locate the suprapatellar fat. If there is no excess to the suprapatellar fat measure 4-6 cm from the knee. With a cosmetic pencil, draw a horizontal line and record its distance from the floor. Extend the measuring tape around the leg. Position the tape in a horizontal plane at the level of the measurement mark. Check that the tape sits parallel to the floor and lies snug but does not compress the skin. Always position the zero end of the tape below the section containing the measurement value. Take the measurement in centimeters to the nearest 0.1 cm (one digit after the decimal point). The technician will take three measurements of leg circumference. When the measurement is measured the same twice (±0.5cm), that measurement will be used. If measurement are taken and all three are different, a fourth measurement will be taken until the same measurement is achieved twice.

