6.1.16.2.2. Local Fat Reduction

Local fat reduction in all subjects will be evaluated by ultrasound. Local fat reduction is defined as the reduction in nodules size and/or numbers in the injected area as compared to baseline. Ultrasound will be evaluated in all subjects at baseline and at Day 28.

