6.1.16.2.3. Duration of the fat reduction effect

The duration of the local fat reduction in all subjects will be evaluated by ultrasound and by leg circumference above the knee in lipedema subjects at Day 56 compared to baseline and to Day 28.

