10.2.2. Secondary Efficacy Endpoints

Secondary efficacy endpoints include:

- For lipedema subjects - The reduction in local subcutaneous fat in the injection site region as compared to baseline based on ultrasound (reduction in nodules size and/or numbers) and leg circumference above the knee assessments.
- For Dercum's disease subjects - The reduction in local subcutaneous fat in the injection site region as compared to baseline based on ultrasound (reduction in nodules size and/or numbers).
- Extended duration of the fat reduction effect. To that end, ultrasound images and above the knee circumference measurement will be followed for 56 days.
- Elucidation of the tissue changes by ultrasound of the injection site to include reduction in fat thickness and nodular quality.

- Improvement in local pain as measured by Comparative Pain Scale and by the reduction in the use of analgesics.
- Improvement in QOL and function in lipedema subjects as measured by questionnaire (such as LEFS).

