5.8.10 Demographic and Baseline Characteristics

5.8.11 Baseline will be defined as the last available and evaluable parameter value before and closest to the injection. If a rechecked value is used for baseline, it should be collected under the same conditions as for the planned baseline.

5.8.12 Baseline safety data will be presented along with subsequent safety values assessed during or after dosing.

5.8.13 The incidence of intolerable side effects will be presented overall and by cohort along with two sided 95% exact binomial Confidence Interval (CI).

5.8.14 Percent changes from baseline in local fat reduction (circumference of the leg above the knee, nodules size and/or numbers in the injected area) and tissue changes (fat thickness), will be presented in tabular form by visit.

5.8.15 Changes in nodular quality, local pain, quality of life and function will be presented in tabular form by visit and cohort.

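### Local fat reduction is defined as any decrease from baseline, with no allowance for measurement error and no subject-level rule

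*Protocol*

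**What the plan says.** Protocol 4.2 lists local fat reduction as secondary endpoints 1 (lipedema) and 2 (Dercum's disease), and its duration as endpoint 3.

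- **Circumference, lipedema (Protocol 6.1.16.2.1):** "A local fat reduction is defined as a reduction (compared to baseline) in the circumference of the leg above the knee".
- **Ultrasound, all subjects (Protocol 6.1.16.2.2):** "Local fat reduction is defined as the reduction in nodules size and/or numbers in the injected area as compared to baseline".
- **Duration (Protocol 6.1.16.2.3)** uses the same measures: "The duration of the local fat reduction in all subjects will be evaluated by ultrasound and by leg circumference above the knee" (the latter in lipedema subjects), at Day 56 against baseline and Day 28.
- **Tape measurement (Protocol 6.1.13):** the resolution is fine, "Take the measurement in centimeters to the nearest 0.1 cm (one digit after the decimal point", but the agreement rule is wider: "When the measurement is measured the same twice (±0.5cm), that measurement will be used". It does not say which of two agreeing readings is recorded.
- **Analysis (Protocol 10.5.5 and SAP 5.8.14):** "Percent changes from baseline in local fat reduction (circumference of the leg above the knee, nodules size and/or numbers in the injected area", with fat thickness, are to be tabulated by visit. No threshold or subject-level rule is added. The only interval specified for a named endpoint is the exact binomial one for intolerable side effects (Protocol 10.5.4, SAP 5.8.13).

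**The concern.** Read literally, the definition depends only on the sign of the change. A circumference fall of 0.1 cm is a fat reduction under 6.1.16.2.1, while 6.1.13 treats two readings 0.5 cm apart as the same. Measurement noise alone will therefore put many readings on the favourable side.

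The definition also stops at the reading. Each lipedema subject has two treated legs and each Dercum's subject at least two injected nodules. Nodule size may be a diameter or a surface in three dimensions, and there are two follow-up days. Nothing says how these become one result per subject, and the and/or in 6.1.16.2.2 leaves room for any favourable component to count.

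The trial is open label and single arm, with 6 subjects per cohort. If the report says that local fat reduction was seen in a given number of subjects, the plan gives the reader no chance rate to compare it with.

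**Working it through.** The plan states no response rate, power or measurement SD, so there is no figure of its own to reproduce. The check asks how often the definition is met when nothing has changed.

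**Inputs from the documents**
- Rule: any fall counts (Protocol 6.1.16.2.1, 6.1.16.2.2).
- Resolution 0.1 cm, agreement tolerance 0.5 cm (6.1.13).
- Two treated legs per lipedema subject (3.3.1).
- Two to four nodules per Dercum's subject: the minimum is inclusion criterion 2; the maximum is 8 injections (8.4.2) at 2 or more per nodule, 8/2 = 4.
- 6 subjects per cohort, no control (10.3, 6.2.2).

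**Assumptions:** per-visit circumference SD 0.2 to 0.5 cm, symmetric error, no drift; between-leg correlation of change (rho) 0 to 0.8.

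**1. One leg, one visit.** P(fall) = (1 − P(tie))/2, with ties from rounding to 0.1 cm (simulation, 400,000 draws).

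| SD per visit (cm) | P(tie) | P(fall) | P(fall > 0.5 cm) |
|---|---|---|---|
| 0.2 | 13.9% | 43% | 2.6% |
| 0.3 | 9.4% | 45% | 9.8% |
| 0.5 | 5.6% | 47% | 22% |

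**2. Lipedema subject, one visit.** The result depends on the unstated rule.
- Legs averaged: about 45% to 48% with rounding.
- Either leg: 1 − [1/4 + asin(rho)/(2π)] = 75%, 67%, 60% at rho 0, 0.5, 0.8 for a continuous reading; 53% to 72% with rounding.
- Both legs: 1/4 + asin(rho)/(2π) = 25%, 33%, 40% before rounding.

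**3. Dercum's subject, if any nodule suffices.** With each nodule at 50%, 1 − 0.5^k gives 75%, 88%, 94% for k = 2, 3, 4 independent nodules. At rho 0.5, k/(k + 1) gives 67%, 75%, 80%. For one summary size or the count, 1 − 0.5(1 − q) gives 55% to 65% if the count falls by chance in q = 10% to 30%.

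**4. Four or more of 6 subjects.** Binomial tail with n = 6:

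| Null rate per subject | P(4 or more of 6) |
|---|---|
| 45% | 26% |
| 50% | 22/64 = 34% |
| 67% | 68% |
| 75% | 83% |

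**5. Sensitivity to drift.** A systematic shift of 0.3 SD of the difference moves the single-reading rate from 50% to 62% (downward) or 38% (upward, as with swelling).

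**6. What the 0.5 cm tolerance achieves.** The last column of the first table shows that it cuts the single-leg rate to 2.6% to 22%. A limit of 1.96 × √2 × SD, which holds it at 2.5%, would be 0.55 cm (SD 0.2) to 1.39 cm (SD 0.5). The tolerance is thus a floor, not a full error limit.

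**The case against.** The strongest reply is that no responder analysis is planned. Protocol 10.5.5 and SAP 5.8.14 plan percent change by visit, and the SAP table list gives levels, reductions and relative changes, with no table of the proportion reduced. On that view 6.1.16.2.1 and 6.1.16.2.2 merely name the variable. This stands in large part and limits the impact. It does not remove the point: Protocol 4.2 refers to 6.1.16.2.1 as the endpoint's definition, and that definition is yes or no. The SAP also lists shift tables for fat thickness and the additional measurements (Listings 16.2.5-3-5 and 16.2.5-3-8) without defining categories.

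Several stronger readings are tempting, and the documents do not support them.

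- **That more than half of subjects would qualify by chance.** This needs an any-leg, any-nodule or any-component rule, which is neither stated nor excluded. Section 6.1.16.2.1 has no and/or, and Protocol 10.2.2 joins the lipedema measures with and: "based on ultrasound (reduction in nodules size and/or numbers) and leg circumference above the knee assessments".
- **That reduction in most subjects is the expected result of an inert injection.** At null rates of 45% to 50%, 4 or more of 6 occurs with probability only 26% to 34%. The 83% figure needs two independent indicators at 50% each.
- **That the trial cannot tell an active drug from an inactive one because of this definition.** The continuous data are still collected. Lack of attribution comes mainly from having no control arm, and a noise threshold would not remove drift or swelling.
- **That phase 0 counted reductions in the same way.** The drop that "in RZL-012 treated subject of cohort 3 was evident in 5 of 6 treated subjects" was in a treated/control MRI ratio, in a vehicle-controlled study, and was reported as not statistically significant.

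It is also fair to say that the Dercum's shells already separate lipoma number (Tables 14.3-4-1 to 14.3-4-3) from size (14.3-4-4 to 14.3-4-6), and that ultrasound error is not quantified here.

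**Conclusion.** The concern holds in a limited form. The stated definition labels circumference falls inside the protocol's own tolerance as fat reduction, and it has no rule for reaching a subject-level result. With no effect, about 43% to 47% of single-leg readings qualify. At subject level the rate is about 45% to 48% if the legs are averaged and 53% to 72% if either leg suffices.

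These figures rest on an assumed per-visit SD of 0.2 to 0.5 cm and symmetric error without drift; the either-leg range also rests on an assumed between-leg correlation of 0 to 0.8. The documents supply none of these values.

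The planned continuous summaries are not invalidated. What is affected is any statement that a subject or cohort showed local fat reduction, and the duration statement built on it, because no control arm or noise benchmark stands beside it. This is a cheap improvement to make, not a flaw that undermines the trial.

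**What to change.** Amend Protocol 6.1.16.2.1 and 6.1.16.2.2 and SAP 5.8.14 as follows.

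1. Base the fat-reduction statement on the subject-level mean change from Day 0, with legs or nodules averaged within subject, and give a two-sided 95% confidence interval. Name one size metric, and report nodule size and nodule number separately.
2. Tabulate the Screening-to-Day 0 change in leg circumference and in Dercum's nodule size beside the Day 28 and Day 56 changes, as the no-drug benchmark. Both are already measured at Screening and again before injection (Protocol 6.1.13, 6.1.14).
3. Do not call a circumference fall of 0.5 cm or less a reduction, or else state that only continuous change will be reported.

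The cost is a few sentences and an added table column, with no new visits, scans or subjects. There are four drawbacks.

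- Fewer subjects will appear to respond.
- Intervals will be wide: with 6 subjects the half-width is 2.571 × s/√6 = 1.05 s, where s is the between-subject SD of the change.
- The benchmark spans only 2 to 14 days and may understate variation over 28 and 56 days.
- Lipedema nodule size has no such benchmark. Day 0 ultrasound in that cohort is specified only to find nodules for injection, so under the plan's baseline rule (SAP 5.8.11) its change would run from Screening.

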6.1.16.2.2. Local Fat Reduction

Local fat reduction in all subjects will be evaluated by ultrasound. Local fat reduction is defined as the reduction in nodules size and/or numbers in the injected area as compared to baseline. Ultrasound will be evaluated in all subjects at baseline and at Day 28.

6.1.16.2.3. Duration of the fat reduction effect

The duration of the local fat reduction in all subjects will be evaluated by ultrasound and by leg circumference above the knee in lipedema subjects at Day 56 compared to baseline and to Day 28.

6.1.16.2.4. Tissue Changes

Tissue changes will be evaluated by ultrasound. Tissue changes are defined as changes in fat thickness and nodular quality at Day 28 and Day 56 as compared to baseline.

6.1.16.2.5. Improvement in Local Pain

Improvement in local pain will be assessed by Comparative Pain Scale and by reduction in the use of analgesics (dose and/or times a day) by Day 28 and Day 56 with comparing to baseline.

6.1.16.2.6. Improvement in Quality of Life and Function

Improvement in QOL and function in lipedema subjects as measured by questionnaire (such as LEFS) by comparing to baseline at Day 28 and Day 56.

6.1.16.3. Compliance Monitoring

Compliance monitoring will include the following procedures:

- Compliance assessment by site coordinator at the study visit, including but not limited to subject questioning.
- Completion of analgesics use diary by the subject.

6.1.16.4. Dispensing of RZL-012 Investigational Product

The RZL-012 investigational product will be dispensed to the study site under monitored conditions by Nextar Ltd. All procedures connected to investigational product's allocation (kits received at site, returned kits) will be properly documented, dated and signed in a designated site folder to allow full product tracking. Source documents will be kept for the duration required by local regulations and ICH-GCP (whichever is longer).

6.1.16.5. Questioning of Study Subjects

Questioning of study subjects during site visits and any unscheduled conversations (e.g., by phone) with site staff will be fully documented in subject file. Whenever possible, subject questioning should include, but not be limited to, inquiring information regarding occurrence and severity of AEs, treatment tolerability and compliance to future scheduled procedures and visits.

6.2. STUDY VISITS

Study visits will be fully documented in the CRF as described in Section 11. Documentation will be completed in a timely manner and within 5 working days to ensure protocol adherence and compliance with ICH-GCP.

6.2.1. Screening Procedures

All information collected and documented during screening procedures will be reviewed to ensure eligibility in reference to study inclusion and exclusion criteria, and fully documented in subject file.

Screening visit should be performed no later than 2 days prior to baseline visit for all cohorts.

Study Screening Day procedures will include the following:

- Informed Consent - Section 6.1.1
- Medical History - Section 6.1.2
- Concomitant Medication - Section 6.1.3
- Physical Examination - Section 6.1.4
- Pain Measurement – Section 6.1.5
- QOL Measurement –Section 6.1.6
- Vital Signs and Measurements - Section 6.1.5
- Serology Assays – Section 6.1.8
- Clinical Laboratory Tests - Section 6.1.9
- ECG - Section 6.1.10

- Draize Score – Section 6.1.11
- Photography of Injected Site – Section 6.1.12
- Leg Circumference – Section 6.1.12
- Ultrasound – Section 6.1.12

Subjects may be rescreened if they were screened and not dosed within 14 days. The following procedures will be performed: Clinical Laboratory Tests (hematology, serum chemistry, and urinalysis), vital signs, Draize score and photography.

6.2.2. Study Randomization

This is an open label study where all subjects will receive the investigational drug (RZL-012).

6.2.3. Study Treatment

6.2.3.1. Treatment with RZL-012 Investigational Therapy

[figure not shown]
RZL-012 is an investigational product supplied as a single dose single treatment injection in multiple sites (2-16) of injections. Before injection, subjects will be advised to keep their regular diet and physical activity.

The injection dosing regimen and technique is crucial for the therapy safety and efficacy. Syringes will be filled with 0.1 mL RZL-012 and the number of syringes will be compatible with the number of injections. All injections will be administered diagonally in 45 °, using a 1 mL Luer-lock syringe and a 30 G x 1/2" needle.

The hole of the needle should be pointing into the fat layer and the injection direction should be towards earth. An attempt to pull the plunger should be made before injecting to ensure that no blood is coming out. If so, the plunger should be pushed down to inject the medicine. The formulation is viscose, therefore resistance is expected while injecting.

[figure not shown]
For Dercum's disease - The 1st cohort will be comprised of subjects with Dercum's disease. Subjects will receive a single treatment in multiple sites (2-8) according to the design below (Figure 2).

Figure 1: RZL-012 Injection Design in Dercum's Disease Subjects

Injections will be diagonally (45°) to the skin surface towards the center of the nodule and the distance between injections in a nodule will be 1 cm (Figure 2).

Figure 2: RZL-012 Injection Sites in Dercum's Disease Subjects

For Lipedema - The 2nd cohort will be comprised of subjects with lipedema with substantial fat above the knee. A grid line will be drawn with a makeup pencil in a horizontal plane (Figure 3) 4-6 cm from the suprapatellar fat and its distance from the floor recorded. An attempt should be made to find palpable nodules along the grid line. The injection sites will be marked in circles with a non-erasable pen. This mark should be intensified upon following visits. Injections will be given in multiple sites (4-8 in each leg), diagonally (45°) to palpable nodules, in the fat above the knee. An attempt should be made to lift the nodule and inject into the middle of the fat-mass. If no nodules are noted in the horizontal plane, drug will be injected into the fatty tissue (in this case small nodules seen in ultrasound will be followed for changes). Injections will be on the same horizontal plane.

Figure 3: RZL-012 Injection in Lipedema

Injections will be spread as much as possible along the grid line and the distance between injected sites (Figure 4) will be:

- At least 3 cm - For subjects receiving 8 and 12 injections.
- At least 2cm - For subjects receiving 16 injections.

Figure 4: RZL-012 Injection Sites in Lipedema Subjects

In lipedema subjects study will be performed in a dose escalation manner:

The first 2 subjects will receive 20mg RZL-012 in 4 injections (0.1mL each) in one leg followed by 20mg RZL-012 (4 injections, 0.1mL each) in the second leg adding up to 8 injections of 40mg RZL-012 ($1/6.25^{\text{th}}$ the NOAEL based on HED from GLP toxicology study).

The next 2 subjects will receive 30mg RZL-012 in 6 injections (0.1mL each) in one leg followed by 30mg RZL-012 (6 injections, 0.1mL each) in the second leg adding up to 12 injections of 60mg RZL-012 ($1/4.688^{\text{th}}$ the NOAEL based on HED from GLP toxicology study).

The last 2 subjects will receive 40mg RZL-012 in 8 injections (0.1mL each) in one leg followed by 40mg RZL-012 (8 injections, 0.1mL each) in the second leg adding up to 16 injections of 80mg RZL-012 ($1/3.125^{\text{th}}$ the NOAEL based on HED from GLP toxicology study).

Within each cohort, dosing of the subjects will progress consecutively from one individual to the other with a minimum of 7-days between subjects to assess safety. This study design will allow the physicians to monitor safety for at least 7 days prior to dosing the next subject. For cohort 2 the decision to proceed to the next dose level will be made after reviewing all safety data collected by Day 14 within 2 ± 1 d of the last dosed subject. The trial will proceed within a cohort provided that no more than one subject experiences intolerable side effects in a cohort, and based on the decision made by the PI and the Medical Monitor.

Each RZL-012 kit contains 1 vial (250 mg/5 mL) corresponding to the number of subjects receiving treatment in each cohort.

RZL-012 will be injected on baseline study visit.

